**Safety:**

Safety evaluations include adverse event (AE) monitoring, physical examinations, vital sign measurements, electrocardiogram (ECG), and clinical laboratory testing (hematology, chemistry, and urinalysis) as a measure of safety and tolerability for the entire study duration.

**Statistical Methods:****Efficacy:**

All efficacy analyses will be carried out using the Full Analysis Set population, which includes all randomized subjects who receive at least one dose of study drug.

**Period 1 Efficacy****Analysis of the Primary and Key Secondary Endpoints:**

For binary endpoints, frequencies and percentages will be reported for each treatment group.

Comparison between upadacitinib group and placebo group will be conducted using the Cochran-Mantel-Haenszel test adjusting for main stratification factors.

For continuous endpoints, the mean, standard deviation, median, and range will be reported for each treatment group. Comparison between upadacitinib group and placebo group will be carried out using the analysis of covariance model with treatment group as the fixed factor, and the corresponding baseline value and the main stratification factors as the covariates.

Non-responder imputation approach will serve as the primary analysis approach for key binary endpoints and multiple imputation will serve as the primary analysis approach for key continuous endpoints.

Sensitivity analyses based on observed cases will also be conducted for key endpoints. The overall type I error rate of the primary and key secondary endpoints will be strongly controlled using sequential testing.

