**Criteria for Evaluation (Continued):****Efficacy (Continued):****Period 1 (Continued)**

Ranked key secondary endpoints (at Week 12) are:

1. Change from baseline in DAS28 (CRP);
2. Change from baseline in HAQ-DI;
3. Change from baseline in Short Form-36 (SF-36) Physical Component Score (PCS);
4. Proportion of subjects achieving low disease activity (LDA) defined as Disease Activity Score (DAS28 (C-reactive protein [CRP])  $\leq 3.2$ ;
5. Proportion of subjects achieving Clinical remission (CR) based on DAS28 (CRP);
6. Proportion of subjects achieving LDA based on CDAI  $\leq 10$ ;

Other key secondary endpoints (at Week 12, if not specified) are:

- ACR50 response rate;
- ACR70 response rate;
- ACR20 response rate at Week 1.

Additional endpoints at all visits are:

- Change from baseline in individual components of ACR response;
- ACR20/50/70 response rates;
- Change from baseline in DAS28 (CRP) and DAS28 (erythrocyte sedimentation rate [ESR]);
- Change from baseline in CDAI and SDAI;
- Change from baseline in morning stiffness (severity and duration);
- Proportion of subjects achieving MCID in change from baseline in HAQ-DI (defined as change from baseline in HAQ-DI  $\leq -0.22$ );
- Proportion of subjects achieving MCID in change from baseline in HAQ-DI (defined as change from baseline in HAQ-DI  $\leq -0.3$ );
- Proportion of subjects achieving LDA or CR based on DAS28 (CRP), DAS28 (ESR), Simplified Disease Activity Index (SDAI), and Clinical Disease Activity Index (CDAI) criteria (see below);
- ACR/EULAR Boolean remission;

	DAS28 (CRP) and DAS28 (ESR)	SDAI	CDAI
LDA	$\leq 3.2$	$\leq 11.0$	$\leq 10$
CR	$< 2.6$	$\leq 3.3$	$\leq 2.8$

- Change from baseline in EQ-5D-5L;
- Change from baseline in SF-36;
- Change from baseline in Functional Assessment of Chronic Illness Therapy-Fatigue (FACIT-F);
- Change from baseline in Work Instability Scale for Rheumatoid Arthritis (RA-WIS).

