**8.0 Statistical Methods and Determination of Sample Size****8.1 Statistical and Analytical Plans**

The primary analysis will be conducted after all subjects have completed Period 1 (Week 12).

Completed and specific details of the statistical analysis will be described and fully documented in the Statistical Analysis Plan (SAP). The SAP will be finalized prior to the database lock for the analysis at the end of Period 1. The statistical analyses will be performed using SAS (SAS Institute Inc., Cary, NC, USA).

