#### **8.1.4.1.2 Key Secondary Efficacy Variables**

Key secondary endpoints are listed in Section [5.3.3.1.2](#).

For binary endpoints, frequencies and percentages will be reported for each treatment group. Similar analyses as for the primary endpoint will be conducted.

For continuous endpoints, the mean, standard deviation, median, and range will be reported for each treatment group. Comparison for the upadacitinib treatment group and the placebo group will be carried out using the analysis of covariance model with treatment group as the fixed factor, and the corresponding baseline value and the main stratification factors as the covariates.

See Section [8.1.4.1.5](#) for imputation methods.

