#### **8.1.4.1.4 Multiplicity Control for the Primary and Ranked Key Secondary Endpoints**

In order to preserve Type I error, a step-down approach will be used to test the primary and ranked key secondary endpoints where statistical significance can be claimed for a lower ranked endpoint only if the previous endpoints in the sequence meet the requirements of significance.

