9.2.3 Key Secondary Efficacy Analyses

Ranked key secondary endpoints (at Week 12) are:

1. Change from baseline in DAS28 (CRP);
2. Change from baseline in HAQ-DI;
3. Change from baseline in Short Form-36 (SF-36) Physical Component Score (PCS);
4. Proportion of subjects achieving LDA based on DAS28 (CRP) ≤ 3.2 ;
5. Proportion of subjects achieving Clinical remission (CR) based on DAS28 (CRP);
6. Proportion of subjects achieving LDA based on CDAI ≤ 10 ;

Other key secondary endpoints (at Week 12) are:

1. ACR50 response rate;
2. ACR70 response rate;
3. ACR20 response rate at Week 1.

For binary endpoints, frequencies and percentages will be reported for each randomized treatment group. Similar analyses as for the primary endpoint will be conducted.

For the major RA continuous endpoints DAS28 and HAQ-DI change from baseline, statistical inference will be conducted using analysis of covariance (ANCOVA) coupled with MI for missing data handling. Specifically, the ANCOVA model will include treatment as the fixed factor, and the corresponding baseline value and the stratification factor country as the covariates. For other continuous endpoints, statistical inference will be conducted using the MMRM model as described in Section 9.1.2, with the main stratification factor being country. From both the MI and MMRM analyses, the LS mean and 95% CI will be reported for each randomized treatment group; the LS mean treatment difference and associated 95% CI and p-value will be reported comparing upadacitinib group with the placebo group.

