9.2.5 Handling of Multiplicity

In order to preserve Type I error, a step-down approach will be used to test the primary and ranked key secondary endpoints where statistical significance can be claimed for a lower ranked endpoint only if the previous endpoint in the sequence meets the requirements of significance. Specifically, the testing will utilize the endpoint sequence

of primary endpoint followed by ranked key secondary endpoints in the order as specified in Section 9.2.3, using α of 0.05.

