• Proportion of subjects achieving Clinical remission (CR) based on DAS28 (CRP) at Week 12	
 Point estimate, 95% CI and p-value for the treatment comparison between upadacitinib group and placebo group using the Cochran-Mantel-Haenszel test adjusting for stratification factor country. The 95% CI will be based on normal approximation.
• Proportion of subjects achieving LDA based on CDAI ≤ 10 at Week 12	
 Imputation: NRI for primary analysis and OC for sensitivity analysis
• ACR50/70 response at Week 12	
 Analysis Set: FAS
• ACR20 response at Week 1	

Table 7. Summary of Efficacy Variables and Corresponding Analyses for Efficacy Analysis in Period 1 (Continued)

Efficacy Variables	Analysis Method
Key Secondary Variables (continued)	
Continuous Endpoints:	
• Change from baseline in DAS28(CRP) at Week 12	
 LS mean, and 95% CI within each treatment group and LS mean, 95% CI and p-values between upadacitinib group and the placebo group using ANCOVA model with treatment, country and baseline value as covariates. Imputation: MI Analysis Set: FAS
• Change from baseline in SF-36 Physical Component Score (PCS) at Week 12	
 LS mean and 95% CI within each treatment group and LS mean, 95% CI and p-values between upadacitinib group and the placebo group using MMRM model with fixed effects of treatment, visit and treatment-by-visit interaction, country and baseline value as covariate. Analysis Set: FAS
Additional Variables (Summarized at all Visits up to Week 12)	
Binary Endpoints:	
• ACR20/50/70 response rate	
 Point estimate and 95% CI of the response rate for each treatment group. The 95% CI will be based on normal approximation.
• Proportion of subjects achieving change from baseline in HAQ-DI ≤ -0.22 for subjects with baseline HAQ-DI ≥ 0.22	
 Point estimate, 95% CI and p-value for the treatment comparison between upadacitinib group and the placebo group using the Cochran-Mantel-Haenszel test adjusting for stratification factor country. Only nominal p-value will be provided, and the 95% CI will be based on normal approximation.

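### The synopsis promises strong type I error control for all key secondary endpoints, but the step-down leaves out three of the nine: ACR50, ACR70 and Week 1 ACR20

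*Protocol*

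**What the plan says.** The synopsis, under Statistical Methods for Period 1 efficacy, states: "The overall type I error rate of the primary and key secondary endpoints will be strongly controlled using sequential testing". It does not limit this to ranked endpoints.

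Three lists define the key secondary endpoints, and they agree: the synopsis (Criteria for Evaluation), Protocol 5.3.3.1.2 and SAP 9.2.3. Each gives six ranked endpoints: change in DAS28(CRP), HAQ-DI and SF-36 PCS, then LDA by DAS28(CRP), CR by DAS28(CRP), and LDA by CDAI. Each then gives a second list, headed "Other key secondary endpoints (at Week 12, if not specified) are" in the protocol and "Other key secondary endpoints (at Week 12) are" in the SAP. That list holds ACR50, ACR70 and ACR20 at Week 1.

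The operative multiplicity text is narrower than the synopsis. Protocol 8.1.4.1.4 says that "a step-down approach will be used to test the primary and ranked key secondary endpoints". SAP 9.2.5 sets out the sequence "of primary endpoint followed by ranked key secondary endpoints in the order as specified in Section 9.2.3", at alpha 0.05.

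For binary key secondary endpoints, Protocol 8.1.4.1.2 says: "Similar analyses as for the primary endpoint will be conducted". In the Key Secondary block of SAP Table 7, "ACR50/70 response at Week 12" and ACR20 at Week 1 stand beside ranks 4 to 6, with a Cochran-Mantel-Haenszel p-value and no qualifier.

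**The concern.** Read with the protocol's own definitions, the synopsis sentence states a property that the testing procedure does not have for three of nine endpoints. Someone who relies on the synopsis would take a p-value below 0.05 for ACR50, ACR70 or Week 1 ACR20 as a controlled finding. Someone who relies on SAP 9.2.5 would not.

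The question is likely to arise in practice. SAP 4.4 says that the Week 12 analysis is for regulatory submission, and at the rates in Protocol Table 1 both ACR50 and ACR70 would very probably fall below 0.05. Their status should be fixed before the results are seen.

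**Working it through.** **1. Does the bare term key secondary mean only the ranked endpoints?** Protocol 8.2 and SAP 4.3 claim at least 90% power for most of the key secondary endpoints and name ACR50 among them. ACR50 is one of the unranked three, so the unqualified term includes them. Where the documents mean ranked (8.1.4.1.4 and SAP 9.2.5), they say so.

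**2. Could the numbering in SAP 9.2.3 place the three in the sequence?** The SAP numbers them 1 to 3, but in a separate list that restarts at 1 under the heading Other. SAP 9.2.5 refers only to the order of the ranked endpoints. The protocol lists the three as bullets. They have no rank.

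**3. The plan's own figure: 5% for the sequence.** In a fixed sequence at 0.05, a false positive requires rejecting the first true null in the order, which is tested at 0.05. Family-wise error over the primary and ranks 1 to 6 is therefore at most 5% under any configuration. The claim holds for those seven tests.

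**4. What if the three were claimed at two-sided 0.05 outside the sequence?** No document states this rule; the calculation only shows what the misreading would cost. Under the global null, ranks 1 to 6 add nothing, because they are reached only after a false positive on the primary. The family is then four tests.

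The Week 12 correlations follow from nesting (SAP 9.4.1: ACR70 within ACR50 within ACR20) and the Protocol Table 1 rates. With p_r the rarer and p_c the commoner response rate, the correlation is √[p_r(1 − p_c) / (p_c(1 − p_r))].

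| Pair | Placebo (36/15/6%) | 15 mg (64/38/21%) |
|---|---|---|
| ACR50 and ACR70 | √(0.06×0.85 / (0.15×0.94)) = 0.601 | √(0.21×0.62 / (0.38×0.79)) = 0.659 |
| ACR20 and ACR50 | √(0.15×0.64 / (0.36×0.85)) = 0.560 | √(0.38×0.36 / (0.64×0.62)) = 0.587 |
| ACR20 and ACR70 | √(0.06×0.64 / (0.36×0.94)) = 0.337 | √(0.21×0.36 / (0.64×0.79)) = 0.387 |

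The documents give no correlation for Week 1 ACR20. It was assumed to be 0, 0.3 or 0.6 with every other test. Simulation of multivariate normal statistics (6,000,000 draws, |z| > 1.96) gave the probability of at least one false positive:

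| Family | Correlations from | Week 1 corr. 0 | 0.3 | 0.6 |
|---|---|---|---|---|
| The three | placebo | 13.3% | 12.9% | 11.8% |
| The three | 15 mg | 13.1% | 12.7% | 11.6% |
| Primary plus three | placebo | 16.8% | 16.3% | 14.8% |
| Primary plus three | 15 mg | 16.4% | 16.0% | 14.6% |

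Under independence the values would be 1 − 0.95³ = 14.3% and 1 − 0.95⁴ = 18.5%.

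**5. Would the question arise?** Stand-alone power uses 161 × 0.9 ≈ 145 per arm, a pooled-variance normal approximation and the Table 1 rates. ACR50, 38% against 15%: pooled SE 0.0518, unpooled SE 0.0500, Φ[(0.23 − 1.96×0.0518)/0.0500] = 99.5%. ACR70, 21% against 6%: 96.6%.

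**The case against.** The strongest reply is that the plan already settles the matter. The synopsis itself separates ranked from other key secondary endpoints, and only endpoints with an order can be tested sequentially. The heading of Protocol 8.1.4.1.4 is limited to the primary and ranked endpoints, SAP 9.2.5 gives the sequence and alpha, and Protocol 8.1 defers analysis detail to the SAP. On that reading the three are nominal and the synopsis is short by one word.

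Much of this stands. The operative sections are clear and agree, and nominal is the natural reading. It does not rescue the synopsis sentence, which is wrong for the family it names. Nor does any sentence give the status of the three as key secondary endpoints.

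A second reply concerns SAP Table 7. A reader might infer that the table labels these three inconsistently, because the same comparisons recur in the Additional block, where binary p-values are called nominal. The documents do not support treating that as a defect peculiar to the three. The Additional block summarises every visit up to Week 12, so its ACR20/50/70 row also contains the primary, and its LDA/CR row contains ranks 4 to 6. Taken literally, the label would make those nominal too, against SAP 9.2.5. In the available text the label also sits beside the HAQ-DI rows, so its exact reach in the table layout is uncertain. This reply stands in full.

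**Conclusion.** The synopsis sentence is wrong as written. Strong control holds for the primary and six ranked key secondary endpoints, and not for ACR50, ACR70 and Week 1 ACR20. The error is in the description of the procedure; the tests in the sequence are sound.

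Two stronger conclusions should not be drawn. First, a reader might infer that the trial's confirmatory error rate is inflated. It is not: the primary and ranks 1 to 6 stay at 5%, and if the three are nominal no controlled claim is affected. Second, a reader might take 12 to 13% (the three) or 15 to 17% (with the primary) as the size of the defect. Those figures describe unconditional testing at 0.05, which no document proposes; the synopsis itself speaks of sequential testing. They also rest on the global null, on correlations from the earlier study's rates, and on an assumed Week 1 correlation of 0 to 0.6.

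The correction is worth making because it decides what may be claimed for three prominent endpoints in a regulatory submission.

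**What to change.** Before the Period 1 database lock:

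- **Synopsis.** Insert *ranked* before key secondary endpoints in the type I error sentence.
- **SAP 9.2.5.** Add one sentence: ACR50 and ACR70 at Week 12 and ACR20 at Week 1 are outside the testing sequence and their p-values are nominal.
- **SAP Table 7, Additional block.** Exempt the primary and ranks 4 to 6 at Week 12 from the nominal label. Do not add that label to SAP 9.2.4 without the same exemption, because its binary paragraph covers those endpoints too.

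The cost is wording only. No analysis, alpha or sample size changes.

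**Alternative, only if formal claims on the three are wanted.** Append them in a pre-specified order after rank 6, in SAP 9.2.3 and 9.2.5 and in the protocol synopsis, 5.3.3.1.2 and 8.1.4.1.4, and exempt them from the nominal label as well. This takes no alpha from earlier tests. The price is that a claim on any of the three needs all seven earlier tests to succeed, so the stand-alone power values above become upper limits. Power within the sequence cannot be computed from the documents: SAP 4.3 does not name HAQ-DI (rank 2) or CDAI LDA (rank 6) among its powered endpoints and gives no assumed effects for them.

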**Long-Term Efficacy for Period 1 and Period 2 Combined**

Long-term efficacy by time point will be summarized using descriptive statistics.

**Pharmacokinetic:**

A non-linear mixed-effects modeling approach will be used to estimate the population central values and the empirical Bayesian estimates of the individual values of upadacitinib oral clearance (CL/F) and volume of distribution (V/F). Additional parameters may be estimated if useful in the interpretation of the data.

**Statistical Methods (Continued):****Safety:**

Safety analyses will be carried out using the Safety Analysis Set, which includes all subjects who receive at least one dose of study drug. Analyses will be conducted for Period 1 alone, as well as for Period 1 and Period 2 combined. Safety will be assessed by AEs, physical examination, laboratory assessments, ECG and vital signs. Frequency tables and lists of subjects with treatment-emergent AEs by preferred term as in the Medical Dictionary for Regulatory Activities dictionary, by system organ class, by severity, and by relationship to the study drug as assessed by the Investigator will be provided. The changes from baseline in vital signs, physical examination results, and clinical laboratory values will be analyzed in a descriptive manner. Shift of laboratory values from baseline to defined time points will be tabulated.

**1.3****List of Abbreviations and Definition of Terms****Abbreviations**

ACR	American College of Rheumatology
AE	adverse event
ALC	absolute lymphocyte count
ALT	alanine transaminase
ANC	absolute neutrophil count
anti-CCP	anti-cyclic citrullinated peptide
AST	aspartate transaminase
AUC	area under the plasma concentration-time curve
BCG	Bacille Calmette-Guérin
bDMARD	biological disease-modifying anti-rheumatic drug
BID	twice daily (Latin: bis in die)
BUN	blood urea nitrogen
CBC	complete blood count
CD4, CD8	cluster of differentiation
CDAI	clinical disease activity index
CL/F	apparent clearance
C max	maximum plasma concentration
C min	minimum plasma concentration
CPK	creatine phosphokinase
CR	clinical remission
CRF	case report form
CRP	C-reactive protein
csDMARD	conventional synthetic disease-modifying anti-rheumatic drug
CSR	clinical study report
CXR	chest x-ray
CYP	cytochrome
DAS	disease activity score
DMARD	disease-modifying anti-rheumatic drug
DMC	Data Monitoring Committee
DNA	Deoxyribonucleic acid
ECG	electrocardiogram

eCRF	electronic case report form
EDC	electronic data capture
ePRO	electronic patient-reported outcome
EQ-5D-5L	EuroQoL-5D-5L
ESR	erythrocyte sedimentation rate
EU	European Union
EULAR	European League Against Rheumatism
FACIT-F	Functional Assessment of Chronic Illness Therapy – Fatigue
FAS	full analysis set
FSH	follicle-stimulating hormone
GCP	Good Clinical Practice
GFR	glomerular filtration rate
HAQ-DI	Health Assessment Questionnaire – Disability Index
HAV-IgM	Hepatitis A virus immunoglobulin M
HBc Ab/anti-HBc	Hepatitis B core antibody
HBs Ab/anti-HBs	Hepatitis B surface antibody
HBs Ag	Hepatitis B surface antigen
HBV	Hepatitis B virus
HCV	Hepatitis C virus
HCV Ab	Hepatitis C virus antibody
HDL-C	high-density lipoprotein cholesterol
HIV	human immunodeficiency virus
hsCRP	high-sensitivity C-reactive protein
ICF	informed consent form
ICH	International Conference On Harmonization
IEC	independent ethics committee
IGRA	interferon-gamma release assay
INR	international normalized ratio
IR	immediate release
IRB	institutional review board
IRT	interactive response technology
IUD	intrauterine device
IUS	intrauterine hormone-releasing system
JAK	Janus activated kinase

LDA	low disease activity
LDL-C	low-density lipoprotein cholesterol
MACE	major adverse cardiovascular event
MCID	Minimum clinically important difference
MDRD	modification of diet in renal disease
MedDRA	Medical Dictionary for Regulatory Activities
MRB	Minimal Residual B-cells
MTX	methotrexate
MTX-IR	methotrexate inadequate responder
NA	no assessment
NK	natural killer
NKT	natural killer-T
NMSC	non-melanoma skin cancer
NONMEM	non-linear mixed-effects modeling
NRI	non-responder imputation
NRS	numerical rating scale
NSAID	non-steroidal anti-inflammatory drug
OC	observed cases
PCR	polymerase chain reaction
PCS	physical component score
PD	premature discontinuation
PhGA	Physician's Global Assessment of Disease Activity
PK	pharmacokinetic
PPD	purified protein derivative
PRN	as needed (Latin: pro re nata)
PRO	patient-reported outcome
PT	preferred term
PtGA	Patient's Global Assessment of Disease Activity
QD	once daily (Latin: quaque die)
RA	rheumatoid arthritis
RA-WIS	Work Instability Scale for Rheumatoid Arthritis
RAVE ®	EDC system from Medidata
RBC	red blood cell
RCT	randomized controlled trial

RNA	Ribonucleic acid
SAE	serious adverse event
SAP	statistical analysis plan
SDAI	Simple Disease Activity Index
SF-36	Short Form-36
SJC	swollen joint count
SOC	system organ class
T2T	treat-to-target
TA	Therapeutic Area
TB	tuberculosis
TEAE	treatment-emergent adverse event
TJC	tender joint count
TNF	tumor necrosis factor
TNF-IR	tumor necrosis factor inadequate responder
TRUST	Toluidine Red Unheated Serum Test
Tyk2	Tyrosine kinase 2
ULN	upper limit of normal
V/F	apparent volume of distribution
VAS	visual analog scale
WBC	white blood cell

### 3.0                   Introduction

#### **Rheumatoid Arthritis**

Rheumatoid arthritis (RA) is a chronic systemic inflammatory disease of unknown etiology. The hallmark feature of RA is an inflammatory process manifested by persistent symmetric polyarthritis of synovial joints which can ultimately lead to bone erosions, deformity, and disability. Left untreated, or inadequately treated, progressive functional impairment with increasing disability occurs leading to a reduction in quality of life. The prevalence of RA in the general population is approximately 1%, and increases with age in both genders, with women being more prone to developing RA than men. Early therapy with disease-modifying anti-rheumatic drugs (DMARDs) is the standard of care, including conventional synthetic DMARDs (csDMARDs) (e.g., methotrexate [MTX], sulfasalazine, hydroxychloroquine, and leflunomide), and biologic DMARDs (bDMARDs) (e.g., anti-tumor necrosis factor [TNF] and non-anti-TNF biologics).

The European League Against Rheumatism (EULAR) recommends a Treat-to-Target (T2T) approach to initiate therapy immediately after diagnosis of RA with a goal of achieving clinical remission (CR) or low disease activity (LDA), as these are associated with improved long-term outcomes. Also, in line with recent advances in early diagnosis, new classification criteria have been developed. The 2010 American College of Rheumatology (ACR)/EULAR classification criteria redefined the paradigm of RA by focusing on features at earlier stages of disease that are associated with persistent and/or erosive disease, rather than defining the disease by its late-stage features.

Despite major progress in the treatment of RA, there still remains a large unmet medical need, as only a small percentage of RA patients reach or maintain a status of LDA or CR over time or need to discontinue due to safety or tolerability issues. Novel therapies are therefore needed to complement the available interventions to address the unmet need.

